10.3 Analysis Datasets

Primary endpoint datasets will be broken down by classifications outlined in the table below.

Primary Endpoint Characteristic

Ethnicity	Hispanic
	Non-Hispanic
Race	American Indian-Alaska Native
	Asian
	Black or African American
	Native Hawaiian or Other Pacific Islander
	White
Socio-economic status	\$35,000 or less
	\$35,000-\$80,000
	\$80,000-\$130,000
	\$130,000-\$200,000
	\$200,000 or higher
Geographic Location	Metropolitan
	Nonmetropolitan

Analysis of secondary endpoint datasets will be analyzed by comparing screening mammography participation rates reported by the clinical site from 2019 to screening mammography participation rates observed after the study.

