5.1 Participant Inclusion Criteria

To be eligible to participate in this study, an individual must meet all the following criteria:

- Female
- 40 to 74 years old
- Able to undergo the informed consent process
- Willingness to comply with all study procedures
- Available for the duration of the study
- In good general health and at average risk for developing breast cancer

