7.3.3 Follow-Up / Final Study Visit

Follow-up Visit (Assessment of Study Endpoints / Safety)

- Site-specific procedures and instructions provided to participants to review assay results: Melody® Scale, Score, and Classification.

Script-reporting results

*I received your test results back, and your Melody® classification is **** (High or Low), and your score is***.*

*According to the scale provided by Namida Lab, Inc., in the range, you fall into of *** to *** ***percent of women had breast cancer and ****were normal.*

(It is up to you and your practice's discretion to make recommendations for the next steps in screening)

*This practice follows the *** guidelines, and for a woman of your age and family history, we recommend a screening mammogram.*

(If your practice typically schedules screening mammograms on behalf of patients, you may offer to do that now.)

A member of the Namida Lab, Inc. clinical team will reach out to you with the next steps for the VIOLA Study.

Final Study Visit

- Site-specific procedures and instructions are provided to participants to complete the exit questionnaire(s).
- Site-specific final instructions to the participant if additional care is required.

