10.1 Statistical and Analytical Plans

An a priori power analysis was conducted using G*Power v3.1.9.2 to determine the minimum sample size required to find significance with a desired level of power set at 0.80 and alpha (a) level at 0.05. Based on this analysis, it was determined that a minimum of 205 participants were required to ensure adequate power for a Pearson's Chi-square Test of Independence. (12, 13, 14) (Appendix L)

Each participant will be required to take an enrollment survey that collects information on race, ethnicity, and socio-economic status. Participant's addresses will be obtained as part of the requisition process for the CLIA lab, from which information on geographic location can be obtained. In addition to the factors listed above, the enrollment survey also collects information on status and type of health insurance, reproductive health, breast health knowledge, prior screening history, and family and personal history of cancer.

The exit survey has been designed to collect information on the participant experience with Melody® and comprehension of the information Melody® relayed through their site clinician. In addition, information is collected on participant's intention to schedule/participate in future screening mammograms and/or change in intention to participate in a previously scheduled screening mammogram.

Data will be analyzed using SPSS Statistics software. To determine the presence of significant changes, Unpaired T-tests or Mann-Whitney U-test will be used with a significance level set at P < 0.05.

Due to the effect of COVID-19 on screening rates, screening mammogram participation rates will be compared to rates reported for the state of Arkansas in 2019.

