10.2 Statistical Hypothesis

Primary endpoint:

- H_0 = Participation rates in yearly screening mammography with the incorporation of Melody® (examined by geographic location, socio-economic status, race, and ethnicity) will not be greater than participation rates recorded in 2019.
- H_1 = Participation rates in yearly screening mammography with the incorporation of Melody® (examined by geographic location, socio-economic status, race, and ethnicity) will be greater than participation rates recorded in 2019.

Secondary endpoint:

- H_0 = Participation rates in yearly screening mammography, with the incorporation of Melody® (examined by clinical sites), will not be greater than participation rates recorded

in 2019.

- H_0 = Participation rates in yearly screening mammography, with the incorporation of Melody® (examined by clinical sites), will not greater than participation rates recorded in 2019.

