10.4 Description of statistical methods

10.4.1 General Approach

For all variables of interest, percent change will be evaluated for statistical significance by Unpaired T-test or Mann-Whitney U-test as appropriate. Statistical significance will be set at $P < 0.05$.

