10.4.2 Analysis of primary efficacy endpoints

Data for primary efficacy endpoints will be presented as follows:

Analysis of Primary Efficacy Endpoints

		VIOLA	2019	Total
Ethnicity	Hispanic	N (% of total for VIOLA)	N (% of total for 2019)	N (% of total)
	Non-Hispanic	N (% of total for VIOLA)	N (% of total for 2019)	N (% of total)

P value		P =?		
Race	American Indian-Alaska Native	N (% of total for VIOLA)	N (% of total for 2019)	N (% of total)
	Asian	N (% of total for VIOLA)	N (% of total for 2019)	N (% of total)
	Black or African American	N (% of total for VIOLA)	N (% of total for 2019)	N (% of total)
	Native Hawaiian or other Pacific Islander	N (% of total for VIOLA)	N (% of total for 2019)	N (% of total)
	White	N (% of total for VIOLA)	N (% of total for 2019)	N (% of total)
P value		P =?		
Socio-economic status	\$35,000 or less	N (% of total for VIOLA)	N (% of total for 2019)	N (% of total)
	\$35,000-\$80,000	N (% of total for VIOLA)	N (% of total for 2019)	N (% of total)
	\$80,000-\$130,000	N (% of total for VIOLA)	N (% of total for 2019)	N (% of total)
	\$130,000-\$200,000	N (% of total for VIOLA)	N (% of total for 2019)	N (% of total)
	\$200,000 or higher	N (% of total for VIOLA)	N (% of total for 2019)	N (% of total)
P value		P =?		
Geographic Location	Metropolitan	N (% of total for VIOLA)	N (% of total for 2019)	N (% of total)
	Nonmetropolitan	N (% of total for VIOLA)	N (% of total for 2019)	N (% of total)
P value		P =?		

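### The comparison with 2019 is unadjusted, takes four factors one at a time and leaves out age, so a different age mix in VIOLA may create or hide a difference in participation

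*Protocol*

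**What the plan says.** Section 10.1 sets the external reference: "screening mammogram participation rates will be compared to rates reported for the state of Arkansas in 2019". For the secondary endpoint, Section 10.3 uses each clinic's own history, "comparing screening mammography participation rates reported by the clinical site from 2019".

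The primary hypotheses in Section 10.2 concern participation "examined by geographic location, socio-economic status, race, and ethnicity". Section 10.3 repeats those four factors: "Primary endpoint datasets will be broken down by classifications outlined in the table below". Section 10.4.1 gives the test: "For all variables of interest, percent change will be evaluated for statistical significance by Unpaired T-test or Mann-Whitney U-test as appropriate". The table shell in Section 10.4.2, introduced by "Data for primary efficacy endpoints will be presented as follows", has a VIOLA column, a 2019 column and one P value per factor, with no cross-classification. The by-site table in Section 10.4.3 is also unadjusted.

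Age enters none of these. Yet Section 5.1 admits women "40 to 74 years old", and the enrollment survey in Appendix D asks every woman for her date of birth. No age range or age standard is given for either 2019 reference.

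**The concern.** Section 4.1 gives Melody to every participant, so there is no concurrent untreated group. Comparability with 2019 has to come from the choice of reference and from the analysis.

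Section 5.3 recruits volunteers from clinics, employers and the general public. Nothing in the design ties their age distribution to that of Arkansas women or of a clinic's patients in 2019. If participation varies with age, a difference in age mix moves the crude comparison even when Melody has no effect. Because the four listed factors are examined singly, each comparison may also carry differences in the other three.

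At stake is the main claim of the study: a rise over 2019 could be due to age mix, or a real rise could be masked by it.

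**Working it through.** **The plan's own figure.** Appendix L uses 50% v 70%, two-sided alpha 0.05 and power 0.80. The pooled-variance formula without continuity correction gives 93 per group, 186 in total. Adding 10% for drop-out gives 186 x 1.10 = 204.6, so 205. The stated figures reproduce, and this point does not change them.

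**Bias from age mix.** Take two age groups, younger (40-49) and older (50-74), and no effect of Melody:

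bias = (younger share in VIOLA - younger share in reference) x (younger rate - older rate)

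Neither factor is in the documents. Assumed here: 30% of VIOLA and 50% of the reference are aged 40-49, a 20-point shift, with a rate gap of 5 to 30 points.

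- Gap 5: (-0.20) x (-0.05) = +1 point
- Gap 10: (-0.20) x (-0.10) = +2 points
- Gap 20 (40% v 60%): (-0.20) x (-0.20) = +4 points
- Gap 30 (40% v 70%): (-0.20) x (-0.30) = +6 points

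Reversing the shares reverses the sign.

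**Chance of a false significant rise, fixed reference.** Normal approximation, reference rate p0 without sampling error, VIOLA's expected rate p1 = p0 + bias. The cut-off is c = p0 + 1.96 x sqrt(p0(1 - p0)/n), and the chance of exceeding it is 1 - Phi((c - p1)/sqrt(p1(1 - p1)/n)). The nominal upper tail is 2.5%. Two sample sizes are used: 205, and 184 (205 x 0.90 = 184.5, rounded down).

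Example, 4 points, n = 184, 54% v 50%: c = 0.50 + 1.96 x 0.03686 = 0.5722; (0.5722 - 0.54)/0.03674 = 0.88; chance about 19%.

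Example, 6 points, n = 184, 61% v 55%: c = 0.55 + 1.96 x 0.03668 = 0.6219; (0.6219 - 0.61)/0.03596 = 0.33; chance about 37%.

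| Bias | n = 184 | n = 205 |
|---|---|---|
| 1 point | 4.6% | 4.7% |
| 2 points | 7.8% | 8.3% |
| 4 points | 19% | 21% |
| 6 points | 37% | 40% |

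For scale, with n = 205 and a 50% reference, an observed excess of 1.96 x sqrt(0.25/205) = 6.8 points is enough for P < 0.05.

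**If the 2019 figure has its own sampling error.** Treated as a two-sample comparison of 184 v 184, biases of 4 and 6 points give about 12% and 21%. With 93 v 93, as in Appendix L, they give about 8% and 13%.

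**Opposite direction.** With a true 10-point rise (50% to 60%), n = 205 and a fixed reference, power is 82% without bias. A bias of -1, -2, -4 or -6 points lowers it to about 74%, 63%, 40% and 21%.

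**The case against.** **An SAP may deal with it.** Covariate adjustment is often left to an SAP, and a table shell does not forbid a supporting analysis. This has some force. However, the protocol itself fixes the factors, the tests and the layout of the primary table, so an SAP that made age part of the primary comparison would depart from Sections 10.2 to 10.4.

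**The plan is not without protection.** Examining rates within race, ethnicity, income and geography is partial stratification, and comparing a clinic with its own 2019 rate holds the clinic constant. That stands: age adjustment is not the only safeguard. Nor would it remove volunteer selection.

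**The age imbalance is not shown.** A reader might infer that a volunteer sample of this size is bound to differ in age from the reference. The documents give no age mix for VIOLA, Arkansas or any site, so only that it may differ can be said. A site's 2019 patients could be quite similar.

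**The results script is weak evidence.** Section 7.3.3 has the clinician say "for a woman of your age and family history, we recommend a screening mammogram". A reader might take this as proof that the recommendation varies with age. The script has the same recommendation for every woman, mentions age only in passing and leaves next steps to the practice. It does not show that participation differs by age.

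**The size is uncertain.** Every input to the bias is assumed, and at the low end the effect is small. The larger percentages also depend on treating the 2019 rate as exact, which is reasonable for a large state figure but not for a small site.

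**Conclusion.** The point holds as a weakness in the chosen analysis. The protocol fixes an unadjusted, one-factor-at-a-time comparison with an external reference and omits age, which it collects and which may differ between the two sides. It states no age range for the reference.

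Under the assumed 20-point shift in mix and 5 to 30 point gap in rate, the bias is 1 to 6 points in either direction. Against a fixed reference the chance of a false rise goes from 2.5% to between about 5% and 37-40%, and is lower when the reference has sampling error. The documents do not show that such a bias will occur, and a small age gap or shift would matter little. They support a recommended change, with medium confidence; they do not support a claim that the comparison is invalid as it stands.

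**What to change.** In Sections 10.1, 10.3 and 10.4.2:

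1. Restrict the 2019 reference to women aged 40-74 and obtain it by age band (for example 40-49, 50-64, 65-74) from the state source and from each site.
2. Compute the expected number of participants by applying the age-band rates to VIOLA's own age distribution, taken from date of birth. Test observed against expected for the state comparison and, in Section 10.4.3, for each site.
3. Keep the four one-factor tables as descriptive.
4. Fit a logistic model with period, age and the listed factors together only if individual 2019 site records and individual VIOLA outcomes exist, collapsing sparse categories. The documents do not show that they do: the exit survey in Appendix J asks each woman's intention, and the provider survey in Appendix K asks for a total of mammograms scheduled.
5. State volunteer selection as a limit that age standardisation does not remove.

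The cost is a request for age-banded 2019 data, which may exist only in coarse bands, and modest extra analysis. Steps 1 and 2 need no further age data from participants, and the target of 205 is unaffected.

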5.2 Participant Exclusion Criteria

An individual who meets any of the following criteria will be excluded from participation in this study:

- Male*
- Currently diagnosed or are receiving treatment for breast cancer
- Have an uninvestigated area of suspicion or concern in their breast

*Note: While Namida Lab, Inc. understands that breast cancer also affects men, there are not enough samples in the repository from men with breast cancer to ensure the accuracy of the results of Melody® for men.

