5.3 Strategies for Recruitment and Retention

Target sample size:

- An a priori power analysis was conducted using G*Power v3.1.9.2 to determine the minimum sample size required to find significance with a desired level of power set at 0.80 and alpha (α) level at 0.05. Based on this analysis, it was determined that a **minimum of 205 participants** were required to ensure adequate power for a Pearson's Chi-square Test of Independence. (12, 13, 14)

The anticipated site participants' accrual rate will vary; all sites and participants will be located within the United States. Participants will be recruited from outpatient clinics, larger employers, and/or the general public. Participant recruitment venues are site-specific, for example, outpatient clinic monthly clinical breast exam events. Potential participants will be identified and approached using inclusion/exclusion criteria and site-specific events and/or communication channels.

While exact recruitment methods will be specific to each site, the material will be made available in versions suitable for flyers, email, post through social media, or distributed by mail. Forward-facing participant recruitment materials have been submitted separately with indications on how it can be personalization to each site.

The VIOLA Study participants are all women due to the development and validation of Melody®. The objectives and endpoints encourage minorities, employee volunteers, economically disadvantaged, and/or a medically underserved population to participate in the VIOLA Study. The justification for involving vulnerable populations is because they are primarily affected by disparities in the healthcare system. Employee volunteers are included because study sites provide current medical care and have a trusted relationship with the employee volunteer as a current patient.

Careful considerations have been included in the study design and recruitment process to ensure minimal harm/risks and maximum participant protection. Participants will have access to translated study materials and access to additional healthcare navigation if needed. Employers will not be notified of study participation or Melody® results; participation or nonparticipation is confidential. Each participant will receive a \$25 Walmart gift card when completing the VIOLA Study, and there is no cost to participate.

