10.4.3 Analysis of the Secondary Endpoints

Analysis of the secondary endpoints will be presented as follows:

Analysis of Secondary Endpoints				
		VIOLA	2019	Total
Site 1	Followed through with screening mammogram	N (% of total for VIOLA)	N (% of total for 2019)	N (% of total)
	Did not follow through with screening mammogram	N (% of total for VIOLA)	N (% of total for 2019)	N (% of total)
P value		P =?		

The analysis will be conducted for each site enrolled in the VIOLA Study.

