 Contraceptive Patch
 Intrauterine device (IUD)
 Vaginal Ring
 None
2. Are you currently using any hormone replacement therapy? (select one)
 Yes No
3. Please select what hormones you are currently taking: (select all that apply)
 Testosterone
 Estrogen
 Progesterone
 Other: _____
4. Hormone replacement medication name if known: _____
5. At what age did your periods begin? _____ (number)
6. Do you still have regular periods? (select one)
 Yes No
7. If you Do Not have regular periods, please select one of the following reasons: (select one)
 Menopause
 Hysterectomy
 Response to Birth Control
 Uterine Ablation
 Other (please describe): _____
 Unknown
8. Do you still have ovaries? (select one)
 Yes No

Section 3: Breast health:

1. Have you ever been told you have dense breast tissue? (select one)
 Yes No
2. Are you currently on, or have you been told, you should be on a high-risk breast cancer screening protocol? (select one)
 Yes No

3. Do you get an annual mammogram for breast cancer screening? (select one)
 Yes No
4. Do you get a bi-annual, every two years, mammogram for breast cancer screening? (select one)
 Yes No
5. When was your last screening mammogram? (enter date or select one)
(mm/dd/yyyy) ____/____/____ Unknown N/A
6. Have you ever received an abnormal screening mammogram? (select one)
 Yes No
7. From your last mammogram, what BI-RADS assessment category was on your mammogram results report? (select one)
 0 - Incomplete - Additional imaging evaluation and comparison to prior mammograms are needed.
 1 - Negative
 2 - Benign (non-cancerous findings)
 3 - Probably benign finding (follow-up in a short time frame is suggested)
 4 - Suspicious abnormality (biopsy should be considered)
 4A - Finding with a low likelihood of being cancer (more than 2% but no more than 10%)
 4B - Finding with a moderate likelihood of being cancer (more than 10% but no more than 50%)
 4C - Finding with a high likelihood of being cancer (more than 50% but less than 95%), but not as high as Category 5
 5 - Highly suggestive of malignancy (appropriate action should be taken)
 6 - Known biopsy-proven malignancy (appropriate action should be taken)
 Unknown

Section 4: Personal history and family history of cancer:

1. Please list below any cancers you have or have had in your lifetime.

No personal history of cancer Personal history unknown

Cancer Type	Year of diagnosis	Treatment	Treatment ongoing

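### The per-site comparison sets consenting, average-risk women aged 40-74 against a site-reported 2019 rate with no stated eligibility match, so who is counted can produce or hide a rise without any Melody effect

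*Protocol*

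**What the plan says.** Section 10.3 of the protocol sets the secondary analysis as "comparing screening mammography participation rates reported by the clinical site from 2019 to screening mammography participation rates observed after the study". Section 10.4.3 lays out the table: at each site, women who did and did not follow through with a screening mammogram, in a VIOLA column and a 2019 column, with a P value. It adds: "The analysis will be conducted for each site enrolled in the VIOLA Study". Section 10.4.1 makes the test an unpaired t-test or Mann-Whitney test at 0.05.

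The VIOLA column is filled by women who pass sections 5.1 and 5.2. They are female, "40 to 74 years old", "In good general health and at average risk for developing breast cancer", and show "Willingness to comply with all study procedures". They are not being treated for breast cancer, and women who "Have an uninvestigated area of suspicion or concern in their breast" are excluded. Section 5.3 gives as an example of a recruitment venue "outpatient clinic monthly clinical breast exam events". For the 2019 column the protocol names only the source, the site. It states no age range, risk level, treatment status or attendance requirement, and no matching or adjustment.

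The protocol also collects each woman's own screening history. Appendix D, Section 3, items 3 to 5 ask about annual and two-yearly habit and then: "When was your last screening mammogram? (enter date or select one". Item 1 of the participant exit survey (Appendix J) asks whether a mammogram was already booked before enrolment. Section 10.1 lists prior screening history among the data collected. No hypothesis, dataset or table in sections 10.2 to 10.4 uses either item.

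**The concern.** A P value comparing two columns bears on Melody only if the women in them would have screened at about the same rate without it. Women who attend a site, accept a breast cancer screening test and agree to all procedures may differ in mammography uptake from the women behind a site's 2019 rate. Some may already have had a mammogram booked, which the exit survey anticipates.

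This is separate from whether Arkansas or the sites supply the 2019 benchmark. The mismatch lies inside the site rate and remains when that rate is used. If sections 10.3 and 10.4.3 are followed exactly, a significant rise at a site could reflect who consented, and a true rise could be masked if the women enrolled are harder to reach than the 2019 group.

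**Working it through.** **The plan's own figure.** Appendix L uses 50% against 70%, two-sided 0.05, power 0.80. Per group, n = [1.96 √(2 × 0.6 × 0.4) + 0.8416 √(0.5 × 0.5 + 0.7 × 0.3)]² / 0.20² = (1.358 + 0.571)² / 0.04 = 93. The total is 186, and 186 × 1.1 = 204.6, rounded up to 205. Both match the protocol.

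**Inputs for the check.**
- Women per site: 205 over 3 sites, about 68. The protocol says three or more sites; an even split is my assumption.
- 2019 site rate: 40%, 50% or 60%. Appendix L uses 50%; the range is an assumption.
- Melody effect: none.
- Participants' own rate without Melody: s = 5, 10 or 15 points above the site's 2019 rate. The documents give no figure, so this is a range.
- Test: the two-proportion z test of Appendix L. On yes/no data the planned unpaired t-test behaves almost identically at this size.

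**(a) 2019 column treated as a sample.** Chance of a significant rise = Φ[(s − 1.96 × SE₀) / SE₁], where SE₀ uses the pooled rate and SE₁ the separate rates. For 50%, s = 10 points and 68 per column: SE₀ = √(0.55 × 0.45 × 2/68) = 0.0853; SE₁ = √[(0.6 × 0.4 + 0.5 × 0.5)/68] = 0.0849; (0.10 − 0.1672)/0.0849 = −0.79; Φ = 0.214.

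**(b) 2019 rate treated as fixed.** A rise is declared when the count exceeds 68 × [p + 1.96 √(p(1 − p)/68)]. For p = 50% that is 42.08, so 43 or more. The binomial chance of 43 or more out of 68 at a true 60% is 0.340.

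Results at one site, over 2019 rates of 40-60%:

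| Selection (points) | 68 women in 2019 | 2,000 women in 2019 | 2019 rate fixed |
|---|---|---|---|
| 0 | 2.5% | 2.5% | 1.9-2.6% |
| 5 | 8-9% | 12-13% | 11-14% |
| 10 | 21-23% | 37-38% | 34-41% |
| 15 | 42-46% | 69-72% | 67-76% |

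**At least one of three independent sites**, 1 − (1 − p)³: with 68 women in each 2019 column, about 23-24%, 51-54% and 80-85%, against 1 − 0.975³ = 7% with no selection. With a fixed 2019 rate, 29-36%, 71-80% and 96-99%, against 6-8% with no selection.

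**Selection in the other direction.** If Melody truly added 20 points but participants started 10 points below the 2019 group, the net difference would be 10 points. With 68 per column the chance of detecting it would be 21-23%, instead of 65-73%.

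**The case against.** The strongest reply has four parts.

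- **Undefined is not unrestricted.** A reader might infer that the 2019 figure covers every woman on a site's books. The protocol does not say that; it leaves the denominator undefined, and a screening participation rate may already mean screening-eligible women. This stands, so the point is only that no match is stated. Some of that detail could sit in an analysis plan not shown here, but the unpaired comparison with a 2019 group is fixed in the protocol itself.
- **Direction.** A reader might infer that the bias must favour Melody. The documents do not support that. Sections 3 and 4 target populations with low screening compliance, and section 2.1 describes ideal patients as perhaps unmotivated for yearly mammography. Selection could run downward.
- **Size.** The fixed-rate figures are the upper end. Appendix L sizes two equal groups, and the size of the 2019 column is not given. Both sets therefore have to be shown.
- **A paired test as the answer.** It is tempting to say that the collected mammogram date allows a before-after McNemar test to carry the conclusion. It does not. Appendix J item 10 records intention, and Appendix K item 15 an aggregate count of women who scheduled. No listed survey records each woman's completed mammogram. A baseline at consent may fall in the COVID-affected period that section 10.1 avoids by choosing 2019. Being up to date is also not the yearly participation named in section 10.2.

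The text *observed after the study* could also be read as a site-wide rate, but a VIOLA column of follow-through counts points to participants. Finally, this is a secondary analysis in a study that claims only association. That limits the stakes but does not make the P value interpretable.

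**Conclusion.** The concern holds in this form: sections 10.3 and 10.4.3 fix an unpaired per-site test between a selected group and a 2019 group for which no eligibility match is stated. The result can therefore show a rise, or miss one, through who is counted.

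With no Melody effect and 10 points of upward selection, a false rise at one site has a chance of about 21-23% (68 women in the 2019 column) to 34-41% (2019 rate fixed), where 2.5% is intended. These figures rest on 68 women per site, a 2019 rate of 40-60% and an assumed amount of selection; the documents supply neither its size nor its sign. They show how sensitive the test is and do not estimate the bias. The point should be corrected, but it does not bear on the primary hypothesis.

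**What to change.** In sections 10.3 and 10.4.3:

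1. Have each site build its 2019 figure only from women with a visit that year who meet the criteria of 5.1 and 5.2 that its records can show: female, 40-74, not under treatment for breast cancer. Use the same yearly-mammogram definition in both columns.
2. Show the VIOLA column also by prior screening status (Appendix D, Section 3, items 3 to 5) and by whether a mammogram was already booked before enrolment (Appendix J, item 1).
3. Limit the site conclusion to association.
4. Optionally add a paired before-after table as supportive only, and only if each woman's completed mammogram is recorded. State its limits: self-report, unknown dates, time trends and a possibly COVID-affected baseline.

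Items 1 to 3 cost one filtered query per site and a few extra table rows. Item 4 needs new data collection. Matching on eligibility does not remove selection through consent, and the breakdown by prior status addresses that only in part.
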